#### ***PRN medications will be permitted***

In addition to the medications taken regularly each day, subjects will be permitted to continue to use PRN pain medications as needed. Subjects who are not using opioids during baseline will be permitted to use any non-opioid medications as prescribed by their physician in addition to over-the-counter medications (e.g., acetaminophen, ibuprofen, etc.) as PRN medications affecting

pain as needed. Subjects who are using opioids during baseline will also be permitted to increase their use of their existing opioid as prescribed by the investigator.

Subjects will also be permitted to use over-the-counter medications as needed for pain (e.g., headache or back pain) unrelated to their post-amputation pain.

PRN medication use will be documented in the diary.

***Non-pharmacologic therapies in use during baseline will be permitted if they do not increase risk to the subject***

Non-pharmacologic therapies, such as physical therapy or other rehabilitative services, that do not interfere with treatment or increase risk to the subject at the opinion of the investigator, are permitted if they are in use during baseline. Therapies, such as diathermy (short wave, ultrasound, and microwave) therapy and water therapy, which increase risk to the subject, are not permitted. Other electrical stimulation therapies (e.g., transcutaneous electrical nerve stimulation [TENS]) are not permitted.

**7.4 Eligibility**

Amputees who meet all of the inclusion and exclusion criteria will be eligible to enroll in the study as subjects.

**7.4.1 Inclusion criteria**

- At least 18 years old
- Traumatic lower extremity amputation(s)
- Healed amputation and healthy residual limb based upon the investigator's evaluation
- Post-amputation pain [REDACTED]
- Able to understand and willing to take part in study and comply with all study requirements

**7.4.2 Additional inclusion criteria (assessed prior to the testing visit)**

[REDACTED] post-amputation pain [REDACTED]

**7.4.3 Exclusion criteria**

- Change of prescribed medications affecting pain [REDACTED] as indicated from subject-reported medication history.
- Beck Depression Inventory (BDI-II) [REDACTED]
- Compromised immune system based on medical history [REDACTED]

- Diabetes Mellitus Types I or II [REDACTED]
- Implanted spinal cord stimulator, cardiac pacemaker/defibrillator or Deep Brain Stimulator
- History of bleeding disorder or subjects who are on antiplatelet or anticoagulation therapies [REDACTED]
- History of valvular heart disease
- Confounding central nervous system injuries and disorders [REDACTED]
- Allergy to all local anesthetic agents [REDACTED]
- Allergy to skin-contact materials [REDACTED]
- History of recurrent skin infections
- Botulinum toxin injection within the last three months in the affected limb
- Steroid injection [REDACTED] in the affected limb
- Subject has participated in any drug or device trial in the past 30 days
- Subject has participated in previous [REDACTED] sponsored Amputee Pain feasibility trial
- Any other condition that may interfere with ability to participate in a clinical trial [REDACTED] as determined by the Investigator
- Prisoners

**7.4.4 Additional exclusion criteria (verified after initial criteria verification)**

- INR > 1.5 for those on warfarin
- Pregnant [REDACTED]

**7.5 Treatment plan**

The study procedures for this protocol are classified according to the following time periods: Baseline, Screening and Lead Placement, Treatment, and Follow-up. [REDACTED]

**7.5.1 Visit 1 - Baseline**

Individuals with one or more lower extremity amputations reporting post-amputation pain [REDACTED] will be considered for enrollment into the study. Individuals will receive a detailed explanation of study specific procedures as well as the risks and benefits of participating in the study. The individual will be asked to sign the approved study consent during this visit. If the individual agrees to participate by signing the consent form, general inclusion/exclusion criteria will be verified and baseline information will be collected and recorded in the case report forms (CRF). Subject ID will be assigned.

The individual's medication affecting pain usage will be reviewed and documented.

[REDACTED]

The individuals who satisfy the preliminary criteria will be asked to complete a [REDACTED] baseline diary to record [REDACTED] for each region of post-amputation pain [REDACTED] the use of medications affecting pain, and the hours of daily prosthetic usage. Individuals must report [REDACTED]

[REDACTED]

[REDACTED]

[REDACTED]

[REDACTED]

#### **[REDACTED] Visit 2 - Lead Placement and Testing [REDACTED]**

Following the baseline visit, individuals who qualify for lead placement [REDACTED] will return to the clinic for placement of the percutaneous leads [REDACTED]

All individuals receiving warfarin therapy will be tested within 2 days prior to the lead placement visit to ensure they meet the inclusion/exclusion criteria with an INR that is not greater than 1.5.

#### **7.5.2.1 Randomization**

Qualifying individuals will be randomized to either Group #1 (Treatment) or Group #2 (Control) using block randomization. [REDACTED]

[REDACTED] [REDACTED]

[REDACTED]

[REDACTED] [REDACTED]

[REDACTED] [REDACTED]

[REDACTED]

[REDACTED]

[REDACTED]

**7.5.2.6 Home Trial or Subject Disposition**

*At the end of Visit 2, the subject will either:*

- 1) proceed to the home trial,*
- 2) return for another Visit 2, or*
- 3) be terminated from the study*

At the end of Visit 2, there are three options:

1. Proceed to home trial:

If all leads were placed, the subject will be prepared to proceed to the home trial.

2. Return for another Visit 2:

If there is not sufficient time to complete lead placement or the testing, or if the Group #1 subject does not respond to stimulation, the investigator may present the subject with the option to return for a repeat lead placement visit.

3. Terminate from the study:

If the subject does not wish to continue with further lead placement, they will be terminated from the study if no adverse events (AE) are noted at the 24-48 hour telephone follow-up. If an AE is noted the subject will be followed until the AE resolves.

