| Additional Exclusion Criteria (verified after initial criteria verification) | 
 
• INR > 1.5 for those on warfarin
 
• Pregnant [REDACTED]
 
   |
| Primary Safety Endpoint  | 
 
• Occurrence of device-related and procedure-related adverse event rates. Adverse events will be assessed at all visits.
 
  |
| Primary Clinical Endpoint  | 
Pain Intensity: [REDACTED] post-amputation pain [REDACTED] that have intensities [REDACTED] during the baseline period and receive treatment with an investigational device will be used to assess the primary efficacy endpoint. All amputees will record [REDACTED] daily post-amputation pain scores [REDACTED] diaries using [REDACTED]. For each individual, [REDACTED] post-amputation pain [REDACTED] during baseline in a leg that receives blinded treatment from an investigational device(s) will qualify to be used in the determination of clinically-meaningful success for that subject throughout the study. Each amputee must have [REDACTED] reduction [REDACTED] to be considered a success in the primary effectiveness endpoint analysis.
 
The primary endpoint of the study compares the proportion of subjects in Group #1 relative to that in Group #2 that achieve [REDACTED] reduction in [REDACTED] post-amputation pain from baseline to the end [REDACTED] of the home trial, examining the statistical superiority of proportion of clinical successes of Group #1 over the proportion of successes of Group #2. The post-amputation pain intensity scores will be determined for each subject by taking the mean of the daily average pain intensity [REDACTED] reported in the [REDACTED] diary at baseline compared to the mean score for the same region(s) of pain reported [REDACTED].
 |
| Secondary Endpoints  | 
[REDACTED] Durability of the treatment effect for average pain intensity [REDACTED]
 
[REDACTED] Durability of the treatment effect for average pain intensity [REDACTED]
 
The following secondary outcomes will be measured [REDACTED]
 
 
• Pain interference [REDACTED]
 
• Pain disability (Pain Disability Index)
 
• Depression (BDI-II)
 
• Analgesic usage
 
• Prosthetic usage [REDACTED]
 
• Subject Satisfaction Survey
 
   |

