**7.5.3 Visit 3 - Telephone Follow-up**

All subjects will receive a Telephone Follow-up 24 - 48 hours after each Visit 2 (Lead Placement) to query for any adverse event (AE). All AEs will be followed until resolution. Subjects who return for Visit 2 but are not eligible to be randomized will not receive a follow-up phone call to assess adverse events following lead placement because they will not have participated in the lead placement procedure.

**7.5.4 Visit 4** [REDACTED]

Subjects will return approximately 1 week after the final Visit 2.

[REDACTED]

[REDACTED]

[REDACTED]

**7.5.5 Visit 5** [REDACTED]

The subject will return approximately 2 weeks after the initial lead placement. [REDACTED]

[REDACTED]

**Visit 6** [REDACTED]

The subject will return approximately 3 weeks after the initial lead placement [REDACTED]

[REDACTED]

**Visit 7** [REDACTED]

The subject will return approximately 4 weeks after the initial lead placement. This visit is identical to Visit 4, [REDACTED]

[REDACTED]

For Group #2 subjects who received replacement leads at this visit, there are three options:

1. Proceed to home trial:

If the subject responds to stimulation [REDACTED]  
the subject will be prepared to proceed to the home trial. [REDACTED]

2. Return for another Visit 2:

[REDACTED]

If there is not sufficient time to complete lead placement or the testing, or if the subject does not respond to stimulation, the investigator may present the subject with the option to return for a repeat lead placement visit.

3. Terminate from the study:

If the subject does not wish to continue with further lead placement, they will be terminated from the study if no adverse events (AE) are noted at the 24-48 hour telephone follow-up. If an AE is noted the subject will be followed until the AE resolves.

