**7.5.11 Visit 11 – EOT**

**8 Weeks Post Lead Placement: lead removal and end of treatment (EOT)**

The subject will return approximately 8 weeks after the initial lead placement. [REDACTED]

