**Visit 12 – conducted 1 week after EOT**

Subjects will return to the clinic 1 week after the end of treatment (EOT). [REDACTED]

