**Risk of skin irritation, infection, or inflammation at the lead exit site**

[REDACTED]

[REDACTED]

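### Subjects who decline further lead placement leave the study after a clear 24-48 hour call, so a later device- or procedure-related event has no visible scheduled means of capture

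*Combined protocol and SAP*

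**What the plan says.** Section 7.5.2.6 gives three outcomes at the end of Visit 2: go on to the home trial, come back for another Visit 2, or leave the study. The third applies when the subject does not want further lead placement. In that case "they will be terminated from the study if no adverse events (AE) are noted at the 24-48 hour telephone follow-up". The only exception is an event already found: "If an AE is noted the subject will be followed until the AE resolves".

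The Visit 7 text in Section 7.5 repeats the scheme: "For Group #2 subjects who received replacement leads at this visit, there are three options". Its third option carries the same rule and the same call.

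Section 7.5.3 describes the call. Each subject receives a "Telephone Follow-up 24 - 48 hours after each Visit 2 (Lead Placement) to query for any adverse event". A repeat Visit 2 therefore brings a further call. Individuals who are not randomized get no call, because they did not undergo the procedure.

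The synopsis states the primary safety endpoint as "Occurrence of device-related and procedure-related adverse event rates. Adverse events will be assessed at all visits". Section 4.3 words it as the occurrence and type of device-related AEs, without naming procedure-related ones, and speaks of documenting AEs that arise during the study.

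Completers have their leads removed at Visit 11, about 8 weeks after initial placement. They return to the clinic 1 week (Visit 12) and 4 weeks (Visit 13) later, and contacts continue to 10 months after end of treatment.

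**The concern.** Safety is a stated objective, and subjects who stop after an incomplete, unsuccessful or repeated placement are informative about procedural risk. After their last procedure they are also the subjects observed for the shortest time. Once the call is clear they have no further visits, and visits are where AEs are assessed. An event that begins on, say, day 5 would be recorded only if the subject or a treating clinician volunteered it and the site still had a way to enter it.

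The protocol's risk section names local events that may matter here, among them "Risk of skin irritation, infection, or inflammation at the lead exit site" and a lead breaking beneath the skin. The text under these headings is redacted, so the documents give no times of onset. That some events first show after 48 hours is an assumption, although the plan itself assesses completers well beyond that point after lead removal.

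What is at stake is the completeness of the safety description in a pilot with up to 54 subjects undergoing lead placement, where one or two related events would be noticeable.

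**Working it through.** There is no figure in the plan to reproduce, because the point concerns ascertainment. The check sets the schedules side by side and then illustrates the possible size.

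**Step 1. Scheduled AE observation after the last lead procedure**

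- Leaves at Visit 2 with a clear call (7.5.2.6, 7.5.3): 24-48 hours, that is 1-2 days.
- Leaves after replacement leads at Visit 7 with a clear call: 1-2 days after the replacement. The original placement has already been followed by Visits 4 to 7, about 4 × 7 = 28 days.
- Completer: first visit 7 days and second visit 28 days after lead removal. Visit 13 falls about 8 × 7 + 28 = 84 days after initial placement.

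Ratio of completer observation to Visit 13 against a stopped subject: 28 / 2 = 14 with the call at 48 hours, and 28 / 1 = 28 with the call at 24 hours.

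**Step 2. Is there another visible route to capture?**

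- AE assessment is tied to visits (synopsis), and a stopped subject has none left.
- Follow-up to resolution (7.5.2.6) requires an event already noted at the call.
- Unscheduled visits (7.5.23) can be prompted by an AE, but nothing visible extends them to someone who has left the study.
- Section 7.6 (Early termination) is redacted, so a later contact there cannot be excluded.

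**Step 3. Illustration of size**

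Let k be the number of stopped subjects, p the risk of a related event in each, and s the share of those events first appearing after the call. The documents give none of these; all three are assumptions. Expected events without a scheduled contact = k × p × s.

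- Low: k = 2, p = 0.10, s = 0.5 gives 2 × 0.10 × 0.5 = 0.1.
- Middle: k = 5 gives from 5 × 0.10 × 0.5 = 0.25 to 5 × 0.30 × 0.9 = 1.35.
- High: k = 8, p = 0.30, s = 0.9 gives 8 × 0.30 × 0.9 = 2.16.

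Over these inputs the range is about 0.1 to 2.2 events. Within each set of inputs it is an upper figure, since some events may be volunteered.

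**The case against.** The strongest objection is redaction. Section 7.6 is blacked out, as are parts of Visits 2 and 7, of Section 4.3, of the unscheduled-visit text and of the risk section. A safety contact could sit in any of them. This stands as a limit: one can say that no scheduled capture is visible, but not that events are missed. It does not remove the point, because the exit rule itself is legible, appears twice, and ends participation on a clear call.

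A second objection is that the comparison is unlike. Completers' post-removal visits follow about eight weeks with leads in place, whereas a Visit 2 leaver never enters the home trial. This also stands in part. The ratio of 14 describes the schedule and is not a ratio of risk.

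Three stronger readings are tempting, and the documents support none of them:

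- A reader might infer that stopped subjects sit in the safety denominator with almost no time at risk and so lower the reported rate. Section 9.5 defines its populations for the effectiveness endpoints, and no safety denominator is visible. Section 9.2 speaks of documenting, reporting and categorizing AEs. Visit 7 leavers also have about four weeks of observation.
- A reader might infer an imbalance between arms, because non-response is named for Group #1 at Visit 2 and appears for Group #2 at Visit 7. Non-response leads to the offer of a repeat visit. Leaving depends on the subject's wish, and lack of time is another route to the repeat visit that is not confined to one group.
- A reader might spread events evenly over 28 days and conclude that nearly all of a stopped subject's events are lost. The documents give no distribution of onset times, so no such percentage can be stated.

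**Conclusion.** The point holds as a gap in AE ascertainment. On the visible text, a subject with a placed or attempted lead who declines further placement has 1-2 days of scheduled observation after the last procedure, and a later device- or procedure-related event has no scheduled means of capture. For Visit 7 leavers this is limited to the replacement procedure.

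The number of events affected cannot be derived from the documents. Under the assumed inputs above it is at most about two and may well be none. The conclusion rests on two conditions: that the redacted Section 7.6 adds no contact, and that some related events first appear after 48 hours. It is worth correcting because correction is cheap, not because a bias of known size has been shown.

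The endpoint wording is a related inconsistency. The synopsis counts device- and procedure-related AE rates, while Section 4.3 names device-related AEs only. The difference matters here because events after a stopped placement may well be procedure-related.

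**What to change.** First check Section 7.6. If it already provides later AE contacts for these subjects, refer to it in 7.5.2.6 and in the Visit 7 text, and the ascertainment point is closed.

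If it does not:

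- State in both places that any subject in whom a lead was placed or attempted stays in AE data collection after stopping. Telephone AE contacts would fall at the plan's existing 1-week and 4-week post-removal time points, counted from the last lead removal or attempt.
- In the safety summary, list these subjects' AEs and length of observation separately.

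In either case, reconcile the primary safety endpoint between the synopsis and Section 4.3, so that it is clear whether procedure-related events are included.

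Treatment and stopping decisions do not change; only the collection and reporting of AEs do. The cost is a short amendment, two telephone calls per stopped subject, and about four more weeks on study for each of them.

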**7.5.2.7 Bilateral Amputees**

*Bilateral amputees may also receive up to 2 SPRINT Systems for their second leg if it meets the same criteria*

**7.5.2.8 Photography and Video Recording**

The lead placement procedure may be photographed or recorded on video for educational, publication, and training purposes. Subject consent will be obtained for photography or video recording; subject faces or any identifying marks either will be de-identified or will not appear in the pictures and video. Ultrasound imaging collected during lead placement may be obtained and provided to the Sponsor.

**7.5.2.9 Home Trial**

*At the end of Visit 2, subjects will be prepared to proceed to the home trial*

Group #1 subjects will be prepared to proceed to the home trial. The stimulation parameters will be set before the subject leaves the visit. [REDACTED]

Group #2 subjects will be prepared for the home trial. The site will ensure the Stimulator is placed in Sham mode before the subject leaves the visit. [REDACTED]

**7.5.3 Visit 3 - Telephone Follow-up**

All subjects will receive a Telephone Follow-up 24 - 48 hours after each Visit 2 (Lead Placement) to query for any adverse event (AE). All AEs will be followed until resolution. Subjects who return for Visit 2 but are not eligible to be randomized will not receive a follow-up phone call to assess adverse events following lead placement because they will not have participated in the lead placement procedure.

**7.5.4 Visit 4** [REDACTED]

Subjects will return approximately 1 week after the final Visit 2.

[REDACTED]

[REDACTED]

[REDACTED]

**7.5.5 Visit 5** [REDACTED]

The subject will return approximately 2 weeks after the initial lead placement. [REDACTED]

[REDACTED]

**Visit 6** [REDACTED]

The subject will return approximately 3 weeks after the initial lead placement [REDACTED]

[REDACTED]

**Visit 7** [REDACTED]

The subject will return approximately 4 weeks after the initial lead placement. This visit is identical to Visit 4, [REDACTED]

[REDACTED]

For Group #2 subjects who received replacement leads at this visit, there are three options:

1. Proceed to home trial:

If the subject responds to stimulation [REDACTED]  
the subject will be prepared to proceed to the home trial. [REDACTED]

2. Return for another Visit 2:

[REDACTED]

If there is not sufficient time to complete lead placement or the testing, or if the subject does not respond to stimulation, the investigator may present the subject with the option to return for a repeat lead placement visit.

3. Terminate from the study:

If the subject does not wish to continue with further lead placement, they will be terminated from the study if no adverse events (AE) are noted at the 24-48 hour telephone follow-up. If an AE is noted the subject will be followed until the AE resolves.

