**7.5.8 Visit 8 – 5 Weeks Post Lead Placement**

The subject will return approximately 5 weeks after the initial lead placement. [REDACTED]

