**7.5.9 Visit 9 – 6 Weeks Post Lead Placement**

The subject will return approximately 6 weeks after the initial lead placement. [REDACTED]

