**9.1 Primary clinical efficacy endpoint analysis**

[REDACTED]

The effectiveness of percutaneous Peripheral Nerve Stimulation (PNS) for the treatment of post-amputation pain will be assessed in the present study. The goal of the proposed [REDACTED] study is to determine if the investigational treatment produces pain relief that is clinically meaningful and greater than the placebo effect. To distinguish between the effect of the investigational treatment and the placebo effect, qualifying individuals will be randomized (1:1) to either Group #1 (Treatment) or Group #2 (Control). The groups will be identical except for whether active stimulation (Group #1) or sham stimulation (Group #2) is delivered during the first 4 weeks of the home trial. Both groups are expected to experience a similar placebo effect from the study procedures and use of the devices. In Group #1, subjects will experience both the placebo effect and the investigational treatment effect. During the sham stimulation phase in Group #2, subjects will experience only the placebo effect. Thus, if there is a difference between the mean improvements during sham stimulation and active stimulation, it can be attributed to the investigational treatment effects.

The null hypothesis ( $H_0$ ) is that the investigational treatment (Group #1, active simulation) is equal to the control (Group #2, sham stimulation) in providing pain relief. The alternative hypothesis ( $H_1$ ) is that Group #1 has a proportion of successes that is not equal to the proportion of successes of Group #2.

1.  $H_0$ : proportion of successes of Group #1 = proportion of successes of Group #2
2.  $H_1$ : proportion of successes of Group #1  $\neq$  proportion of successes of Group #2

If the proportion of successes of the investigational treatment is statistically significantly greater ( $p < 0.05$ ) than the proportion of successes of the control during the first 4 weeks of the home trial and the alternative hypothesis is accepted at the 0.05 level of significance, it will indicate that the investigational treatment is clinically significant and different than the placebo effect.

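### Visit 4 is dated from the final Visit 2 but Visits 5-11 from the initial lead placement, so after a repeat placement a week or more later the visit order and the meaning of week 4 are not fixed

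*Combined protocol and SAP*

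**What the plan says.** Two anchors are used in Section 7.5.

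- Visit 4 (Section 7.5.4): "Subjects will return approximately 1 week after the final Visit 2".
- Visit 5 (Section 7.5.5): "The subject will return approximately 2 weeks after the initial lead placement".
- Visit 6: "The subject will return approximately 3 weeks after the initial lead placement".
- Visit 7: "The subject will return approximately 4 weeks after the initial lead placement".
- Visit 8 (Section 7.5.8): "The subject will return approximately 5 weeks after the initial lead placement". Visit 9 (Section 7.5.9): "The subject will return approximately 6 weeks after the initial lead placement". Visits 10 and 11 follow the same pattern at 7 and 8 weeks.

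Section 7.5.2.6 sends a subject to the home trial once all leads are placed. It offers a repeat placement visit when time runs out, or "if the Group #1 subject does not respond to stimulation". Table 3 labels Visits 4 to 11 as the 1- to 8-week stimulation visits; its windows are redacted.

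The analysis sections use a home-trial clock. Section 9.1 says that active or sham stimulation "is delivered during the first 4 weeks of the home trial". It averages diary scores over those weeks, counting for each leg only days when all its leads are in. Its example is a second leg fitted in week 2, for which weeks 2 to 4 are used. Section 9.3 treats the week before Visit 7 as week 4 of the home trial and the week before Visit 11 as week 8. It also puts sham in weeks 1-4, and Section 9.4 puts active stimulation for Group #2 in weeks 5-8.

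**The concern.** The anchors agree only when there is a single Visit 2. After a repeat, Visit 4 moves with the last session and Visits 5 to 11 do not. Section 7.5.2.6 suggests that a subject whose first session failed has not begun the home trial. Visit 7 could then arrive before that subject has had four weeks of it.

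Two things are at stake. First, opioid use (as morphine equivalents) and prosthetic use are taken from the week before Visit 7, which would then be an earlier home-trial week. Repeats may be unevenly spread: at Visit 2, lack of time can prompt one in either group, but non-response does so only in Group #1. Second, the primary endpoint is a mean over the first four weeks of the home trial, and the visible text does not say which day starts that period after a repeat.

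**Working it through.** **Inputs.** Visit anchors: Sections 7.5.4 to 7.5.11. Repeat Visit 2: Section 7.5.2.6. Four-week period: Section 9.1. Visit 7 as the close of week 4: Section 9.3. Use for up to 60 days: Section 1.0, Indication. The gap g (days from initial to final Visit 2) is not given; the range 0 to 14 is my assumption.

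**Formulas.** Day 0 is the initial lead placement.
- Visit 4 = g + 7. Visit k, for k = 5 to 11, = 7(k - 3), giving days 14, 21, 28, ..., 56.
- Spacing from Visit 4 to Visit 5 = 14 - (g + 7) = 7 - g.
- Days from final placement to Visit 7 = 28 - g.
- If the home-trial clock starts at the final Visit 2, the four weeks end on day 28 + g, which is g days past Visit 7, or g/28 of the window.

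**Reproducing the plan.** At g = 0, Visit 4 is on day 7, Visit 5 on day 14, Visit 7 on day 28 and Visit 11 on day 56, which matches the labels in Table 3.

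| g (days) | Visit 4 | Visit 4 to 5 spacing | Final placement to Visit 7 | End of 4 weeks counted from final Visit 2 | Share past Visit 7 |
|---|---|---|---|---|---|
| 0 | day 7 | 7 d | 28 d | day 28 | 0% |
| 3 | day 10 | 4 d | 25 d | day 31 | 11% |
| 7 | day 14 (with Visit 5) | 0 d | 21 d | day 35 | 25% |
| 14 | day 21 (with Visit 6) | -7 d | 14 d | day 42 | 50% |

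**Week 4 at Visit 7.** The week before Visit 7 covers days 21 to 28, which is 21 - g to 28 - g days after final placement. At g = 7 that is days 14 to 21 (the third week); at g = 14 it is days 7 to 14 (the second week).

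**The plan's own example.** If the second-leg session in week 2 (about days 7 to 13) counts as the final Visit 2, Visit 4 falls on days 14 to 20, on or after Visit 5.

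**Two readings of the blinded period.**
- Clock from the initial placement: the period ends at Visit 7, leaving 28 - g days with all leads in (21 at g = 7, 14 at g = 14). The Section 9.3 definition of week 4 and the Section 9.1 example favour this.
- Clock from the final Visit 2: the period ends g days after Visit 7. Section 7.5.2.6 supports this for a subject whose first session did not lead to the home trial.

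**60-day check.** Counting every visit from the final Visit 2 puts Visit 11 on day 56 + g, beyond day 60 when g > 4 (day 63 at g = 7). This matters for any lead kept from the first session.

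**The case against.** A reader might infer that Group #2's sham period is contaminated with active stimulation. The documents do not support that as stated. Sections 9.1, 9.3 and 9.4 put sham in weeks 1-4 and active stimulation in weeks 5-8 of one home-trial clock, so on that text no active day falls in the window. The only visible rule for late leads shortens the window and does not shift it. Contamination would need both a clock starting at the final Visit 2 and a Group #2 switch at a Visit 7 dated from the initial placement. Nor can the non-response repeats at Visit 2 cause it: they occur in Group #1, which does not switch. If active days did enter the sham mean, they would tend to narrow the group difference if stimulation relieves pain.

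A reader might also infer that any repeat makes visits collide. On nominal days that needs g of at least 7.

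Third, the initial lead placement may mean the first placement episode as a whole, as opposed to later lead replacements. On that reading there is no clash. The visit windows and much of the Visit 2 and Visits 4-7 text are redacted, so a definition may exist there.

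Most of this stands, and it limits the size of the point. It does not remove the mismatch: the visible text uses two anchors, provides for more than one Visit 2, and defines week 4 by Visit 7. The second-leg example does not settle the case of a subject who had not yet entered the home trial.

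**Conclusion.** The point holds as a conflict between stated rules, of minor to moderate severity. For gaps of about a week or more, Visit 4 falls on or after Visit 5. Visit 7 then comes 21 days (g = 7) or 14 days (g = 14) after final placement, so week-4 opioid and prosthetic data may describe an earlier week, possibly more often in Group #1. For the primary endpoint, the likelier consequence is fewer than 28 days with all leads in place. A window running past Visit 7, with active days in Group #2's mean, is a conditional possibility and not a finding.

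This rests on an assumed gap of 0 to 14 days, nominal visit days, and the initial lead placement meaning the first session. Only repeat placements are affected, and neither their number nor the visit windows can be seen.

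**What to change.** Reconcile Sections 7.5.2.6, 7.5.4 to 7.5.11, 9.1, 9.3 and 9.4 so that Visits 4-11, the Group #2 switch and the 4-week analysis window are all counted from one named day, and define the initial lead placement. Check the result against the 60-day statement in Section 1.0. Which day to use is for the sponsor to decide; this review proposes none.

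State in Section 9.1 that Group #2 diary days after the switch to active stimulation are not part of the weeks 1-4 mean.

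The cost is protocol and SAP wording, plus the check against the 60-day statement.
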